11.0 MISCELLANEOUS PATIENTS RISKS

11.1 BLOOD COLLECTION

Subjects with central venous catheters will have extra blood collected for the study when there catheters are being accessed and blood drawn for clinical purposes. As per above, patients with religious (Jehovah Witness) or medical contraindications will not have blood collected. The collection of extra blood for study will prolong the procedure for less than 2 minutes and will not cause any significant discomfort. Subjects without central venous catheters will require venipuncture at each visit (using a needle to draw blood from a vein). This may cause mild pain or a bruise at the site where the blood is to be collected. Occasionally, a person may feel faint during the time of blood collection. The risk for infection is very rare since only sterile one-time equipment will be used. If possible, sample collection will be coordinated with venipuncture for clinical purposes.

11.2 BONE MARROW ASPIRATE & BIOPSY

All research procedures will be coordinated with clinical bone marrow aspirates and biopsies. If there is insufficient specimen available from the bone marrow aspirate, there will be no additional aspirates performed for study purposes only. As such, there is minimal additional risk to this procedure. The research-only biopsy at the end of induction will be coordinated with the routine bone marrow aspirate; the biopsy will be obtained per standard practice using the same skin puncture with minimal prolongation of anesthesia (typically less than 3 minutes) with minimal additional post-operative discomfort due to the addition of the biopsy to the aspirate. Post-operative care routinely includes assessments of discomfort and the clinical care teams will assist in managing this as needed.

11.3 POTENTIAL RISKS OF INTERVENTION

We do not anticipate any risks directly due to the dietary intervention. Subjects may be at risk for syncope, falling and injury during the activity intervention. The PT will design an activity intervention for each subject that will aim to reduce the risk of fall and injury in patients that experience or develop minor difficulties balancing. In-hospital activity interventions will be properly supervised by a PT with vast experience handling pediatric cancer patients undergoing therapy. The potential risks of home-based

activities and methods for reducing risks will be discussed with patients and their families. Changes in weight and body composition are being carefully monitored by both a RD and PT throughout the intervention. Subjects that are unable to adhere to the dietary and/or activity intervention may be at risk for psychological distress (i.e. depression, anxiety, etc.). The treatment team will work to proactively address these risks in each patient through positive discussion and adjustment of the intervention if necessary. Additionally, each patient may be at risk for psychological distress following the introspective nature of the QOL assessment. Psychological distress from any facet of the intervention will be monitored by the treatment team and referred to the psychosocial team if necessary.

11.4 OTHER RISKS

As described above, there is a risk of radiation exposure from DXA scans to pregnant subjects. This risk will be minimized through routine procedures for women of child-bearing age undergoing chemotherapy including a pregnancy test at start of chemotherapy, tests per hospital policy prior to radiology exams, and guidance for adequate birth control or abstinence provided per routine by the primary treatment team. Confidentiality will be maintained to the standards set by Good Clinical Practice including no identification by name in any published research. Despite best efforts, there remains a risk for “breach of confidentiality” of the collected information.

12.0 CRITERIA FOR REMOVAL FROM THERAPY AND OFF-STUDY CRITERIA

12.1 OFF-THERAPY CRITERIA

1. Continuation of the intervention is determined by physician judgment to not be in the best interest of the patient
2. Subject refuses study interventions (but desires to continue with study observations)
3. Subject's BMI decreases to <5th percentile for age- and sex- (or <18.5 for those >20 years)

Subjects who are off study therapy will continue to be followed with collection of laboratory, radiographic, survey, and assessment data unless they meet the criteria for off study (see below).

For off-therapy patients, by family request and/or in response to questions during the assessments, routine clinical guidance for healthy diet and exercise will be provided by the PT and RD.

12.2 OFF-STUDY CRITERIA

1. Death
2. Relapse of Leukemia
3. Change in treatment plan during induction (i.e. during the study intervention) that no longer meets initial eligibility requirements
4. Lost to follow-up
5. Subject withdrawal of consent
6. Study closure

Study Closure: The study will remain open for follow-up only for a period of 5 years from the last day of follow-up for the final subject. During this time, there will be no study-specific visits or tests, but study personnel may contact patients in clinic or via telephone to obtain information relevant to patient health and diet and activity habits, and/or other relevant information that may become apparent throughout the course of the study, including but not limited to interventions performed by other care providers, survival, or relapse. For this purpose, study records and coding information will be maintained in a confidential database as below until study closure.

13.0 STATISTICAL CONSIDERATIONS AND EVALUATION CRITERIA

13.1 SAMPLE SIZE AND STUDY DURATION

Based on available data over a recent 3-year period (2012-2014), we predict at least 43-45 subjects ≥ 10 years of age with HR-ALL patients will be eligible for enrollment during the three year study. We anticipate $>85\%$ of subjects to be enrolled & evaluable for the primary and secondary aim surrounding the Day 29 time-point, for an effective sample size of at least 36 subjects. As of AMD03, additional site(s) were added to gain experience with the study intervention at outside institutions; there is no change to the target study accrual goal of 36 evaluable subjects.

As subjects historically gain body fat during induction irrespective of starting body composition (i.e. both those lean and those overweight/obese gain body fat), we will enroll a goal of 18 overweight/obese and 18 lean subjects on the study to evaluate for an overall effect of the intervention, as well as a differential effect in those “lean” by BMI percentile. We will continuously monitor accrual by weight category with a minimum final target accrual of 14 overweight/obese and 22 lean subjects (40/60) which, as below, preserves our ability to detect an effect on body fat and on the key secondary aim of MRD. For assessment of the delayed endpoints, we expect that 80% of the initial cohort will additionally be evaluable for secondary the aims at the final pre-start of maintenance time-point (due to treatment-related morbidity/mortality/lost-to-follow-up).

13.2 PRIMARY ENDPOINT EVALUATION

The primary endpoint for efficacy is a reduction in gain of body fat percent (per DXA) from diagnosis to the end of induction. From data on 36 patients from the historical cohort at CHLA with DXA scans pre and post induction, there was a significant average fat gain during induction therapy of 5.5 ± 3.3 percent (mean \pm s.d.), $p < 0.001$. Based on a two-sample (36 historical, 36 present study) two-sided t-test with 5% Type I error, there will be at least 90% power to detect a 2.5 percentage point reduction in change in body fat as a result of intervention (e.g. from gain of 5.5 to a gain of 3.0%). Hence, this study has sufficient power to detect subtle, achievable effects on body fat during induction, and will with certainty detect stabilization of or a decrease in body fat during induction.

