3.0 PRELIMINARY DATA

Obesity is a common problem in our patients with ALL.

In our cohort of adolescents with HR-ALL at CHLA, 48% were overweight or obese at diagnosis. Further, from the time of diagnosis to the end of the induction phase, subjects had an ~25% increase in body fat over these first 28 days of chemotherapy alone (from $23.3 \pm 9.1\%$ at time of diagnosis to $33.7 \pm 9.8\%$ at end of induction, $p < 0.001$, Fig. 1). Even more striking, this gain in body fat percentage was present in the entire cohort regardless of starting body composition (Fig 1.). Body fat then increased even further, to a mean of $37.1 \pm 7.9\%$ by the end of Delayed Intensification, following approximately seven months of intensive chemotherapy ($p < 0.001$, not shown). Overall, this increase in body fat represents a gain of 5.2 ± 4.9 kg of adipose tissue over the entire study period. Given our findings that adipose tissue can directly impair chemotherapy efficacy on ALL (32,33), this gain in body fat during such the critical chemotherapy dose-intensive treatment period is very concerning.

[figure not shown]

Fig 1. Body fat percentage measured by DXA scan in 10-21 year old children at diagnosis and end of induction. *** $p < 0.001$

Obesity impacts ALL survival within the first month of treatment. Treatment for childhood ALL generally lasts for 2-3 years. The first month of treatment (induction) is intense including prolonged high doses of steroids, and weekly chemotherapy, and frequent physician visits. Response to induction therapy through clearance of leukemia from the bone marrow as measured by flow cytometry and reported as “minimal residual disease” (MRD) is generally accepted as one of the best predictors of long-term survival (34). Given the association observed between obesity at diagnosis and EFS (1), we examined whether weight status at diagnosis would increase the risk of residual leukemia at the end of induction as measured by MRD. To do this, we retrospectively evaluated the records of 198 children treated at CHLA for B-precursor ALL. We observed that MRD positivity (as defined per COG by MRD with multicolor flow cytometry $\geq 0.01\%$) was increased in children who were overweight or obese (Fig 2 above).

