6.0 STUDY PLAN

6.1 SUMMARY OF STUDY PLAN

Pre-adolescent and AYA patients with newly diagnosed HR-ALL will have dietary and activity preferences assessed by a registered dietician (RD) and physical therapist (PT) at the start of induction.

Subjects will receive an individualized comprehensive dietary and physical activity plan. The RD and PT will devise a personalized dietary and activity intervention aimed at creating a minimum 10% caloric deficit each day (10% nutritional + exercise) throughout the four weeks of induction therapy. Adherence to the intervention will be assessed by the RD and PT at regular weekly intervals at routine clinic visits for chemotherapy and with home phone-calls between clinic visits. Home and hospital activity will also be recorded using a wearable electronic movement monitoring device (Fitbit ®) for all participants. A list of representative “menu” of possible activity interventions from which subjects may choose is provided as a separate Appendix. The primary efficacy of the intervention will be assessed in comparison to a recent historical control via determining the change in body fat percentage (and lean muscle) during induction as quantified by dual-energy x-ray absorptiometry (DXA). A key secondary aim will be the effectiveness of the intervention to reduce chemoresistance as evidenced by decreased prevalence of leukemia minimal residual disease (MRD) at the end of induction. MRD using multicolor flow cytometry is routinely assessed as a predictor of outcome in all patients with HR-ALL. Exploratory analyses will also examine biomarkers of the proposed mechanism including adiposity and intervention-related changes in leukemogenic signaling pathways, oxidative stress, and cellular metabolism. Parent- and subject-reported QOL assessments will consist of the PedsQL and Child and Adolescent Scale of Participation (CASP) surveys (see separate Appendix) and will be conducted pre- and post-induction and at two delayed time-points (mid-point of intensive chemotherapy [3 months from diagnosis] and at end of intensive chemotherapy phase [10 months from diagnosis] to assess the psychosocial benefits of the intervention.

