9.1 REQUIRED OBSERVATIONS

“At Diagnosis” blood samples should be collected before or in closest proximity as possible to starting systemic chemotherapy (steroid pre-treatment, steroid prophylaxis, or intrathecal therapy may have already been given), but all samples must be collected before the start of the activity/nutrition intervention and prior to the end of chemotherapy day 4

The DXA scan should be done in closest proximity to diagnosis as is feasible, but **must be done within 96 hours from the beginning of systemic chemotherapy** and ideally before the start of the activity/nutrition intervention. The timing of the DXA scan in relation to chemotherapy and the intervention will be recorded.

STUDY MEASURE		Diagnosis (Day 1)	Day 8	Day 15	Day 22	End Induction (Day 29)	Start IM#1	Start Maint
Patient History	Clinical History ^{1*}	X	X	X	X	X	X	X
Anthropo-metrics	Height/Weight*	X	X	X	X	X	X	X
	Tricep skin folds	X	X	X	X	X	X	X
	Waist to hip ratio	X	X	X	X	X	X	X
Clinical Assessments	RD Assessment-3 day food log	X				X		
	RD Assessment-24 hr recall	X	X	X	X	X	X	X
	PT Assessment-Complete BOT2	X				X		
	PT Assessment-BOT2 –Brief		X	X	X		X	X
	Fitbit Tracker	Continuous from time of study entry until study end						
Laboratory Tests (blood) ²	Liver function tests ^{3*} (AST/ALT/Bili)	X	X	X	X	X		
	Lipid Panel	X				X	X	X
	[name] Labs	X				X	X	X
	Peripheral blood leukemia blasts ⁴	X						
	Pregnancy Test*	X				X		
Pathology Tests	Bone Marrow Aspirate ^{5*}	X				X		
	Biopsy Marrow Biopsy ⁵	X*				X		

Radiology Tests	DXA Scan	X				X ⁶		
Survey Instruments ⁷	PedsQL - Core	X				X	X	X
	PedsQL - Fatigue	X				X	X	X
	CASP	X				X	X	X

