13.3 SECONDARY ENDPOINTS Evaluation

To compare the rate of leukemia “positive” minimal residual disease (MRD) in the bone marrow at end of induction ($\geq 0.01\%$ mononuclear cells) in those who received the intervention as compared to historical controls.

The key secondary endpoint for efficacy is whether or not the bone marrow is “positive” for MRD at the end of induction (using the COG definition of $\geq 0.01\%$ mononuclear cells). From the retrospective study at CHLA of B-precursor ALL/obesity and end-induction MRD, 69 patients in the cohort had HR-ALL over the age of 10 at diagnosis. Of these, 53% of those overweight or obese (n=30) were MRD positive at the end of induction as compared to only 26% of those lean at diagnosis (n=39). Using this cohort as the historical comparison group, for the overweight/obese subset only, this study will have approximately 80% power to detect a reduction in the MRD positive rate to approximately that of the historical lean group (i.e from 53% to 24%) based on a two-sample, one-sided test of proportions with a Type I error of 0.10 (as a commonly used “go/no go” threshold to continue to Phase III trials). For the overall cohort, again in comparison to the historical cohort (MRD+ 38%, n=26/69) using a similar two-sample, one-sided test of proportions, the study will have the ability at $\sim 80\%$ power to detect a decrease in MRD by 20%. The study will therefore provide data on the potential reduction in the MRD positive rate that can be expected in preparation for the subsequent randomized Phase III trial for efficacy. These analyses will be adjusted for risk group, age, and other factors as appropriate and also compared to external published rates for MRD positivity.

To assess adherence to, and feasibility of, implementing a personalized and comprehensive dietary and exercise intervention during the first month of intensive chemotherapy

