15.0 RECORDS AND REPORTING

Research records will be maintained through paper study-specific case reporting forms (CRF). Research records for this study will be maintained in locked cabinets in the Clinical Trials Office (CTO) or institutional research offices accessible only to the investigators and study team. The master list linking subjects to their unique identifier will be kept in the regulatory binder locked in the CTO office and in a password-protected database. Regulatory binder and CRFs will be maintained primarily by the research coordinator with assistance from the PIs/investigators as needed.

Study results will be entered by each site directly into the secure REDCap database maintained by USC/SC-CTSI. At conclusion of the treatment portion of the study, screening logs with coded identifiers only will be provided from each site to enable assessment of selection bias (e.g. CONSORT diagram). The database will then be downloaded by the study PI for potential further secondary analysis and follow-up as indicated in Section 13.2 (“Study Closure”). The database will remain under unique password-protection and will remain strictly confidential. At the conclusion of the prescribed 5-year follow-up period (final study closure), all identifying information will be destroyed and the database will be preserved in a password-protected completely de-identified format for a minimum of six years as per CCI requirements at which time it will be destroyed.

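### The primary comparison with historical controls names only an unadjusted t-test; a covariate-adjusted primary model should be prespecified

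*Combined protocol and SAP*

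**What the plan says.** Section 6.1 sets the comparison: "The primary efficacy of the intervention will be assessed in comparison to a recent historical control via determining the change in body fat percentage". Section 13.2 gives the endpoint, the mean and SD of change in 36 CHLA controls (5.5 and 3.3 percentage points), and one power sentence: "Based on a two-sample (36 historical, 36 present study) two-sided t-test with 5% Type I error". It contains no separate analysis sentence, model or covariate list.

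The only adjustment statement is in 13.3: "These analyses will be adjusted for risk group, age, and other factors as appropriate". It closes the MRD paragraph, and the rest of that sentence refers to published MRD rates, so it does not reach body fat.

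Two other provisions touch on comparability. Section 15.0 says that "screening logs with coded identifiers only will be provided from each site to enable assessment of selection bias". Section 13.1 says: "We will continuously monitor accrual by weight category with a minimum final target accrual of 14 overweight/obese and 22 lean subjects". Section 13.1 also records that "additional site(s) were added to gain experience with the study intervention at outside institutions".

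The controls are thinly described. Section 3.0 gives a nominal interval ("over these first 28 days of chemotherapy alone") and an age range of 10 to 21 for the earlier CHLA cohort. For the 36 controls, the documents do not give actual scan dates, steroid regimen or sex mix, or say whether the exclusions in 5.2 were applied.

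**The concern.** In a non-randomised comparison, the difference in mean change contains the intervention effect plus whatever the cohorts' other differences contribute. The t-test's 5% error rate covers sampling variation only. The documents show four routes by which the cohorts could differ:

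- **Sites.** The controls are from CHLA alone; study patients may come from added sites.
- **Weight mix.** The study group may run from 14/36 = 39% to 18/36 = 50% overweight or obese. The mix among the 36 controls is not given.
- **Exclusions.** Section 5.2 excludes low BMI and patients judged unable to follow the intervention. It is not stated that the controls were selected in the same way.
- **Steroid exposure.** Section 5.1 sets only a minimum duration, while section 2.2 names glucocorticoids as a likely contributor to fat gain.

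Screening logs and accrual monitoring can reveal or limit some of this, but neither adjusts the estimate. If the t-test is only a device for the power calculation, then 13.2 names no primary analysis. Covariates could then be chosen after the study data are seen, with the control outcomes already known.

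**Working it through.** **Inputs from 13.2.** 36 per cohort; SD of change 3.3; difference 2.5 points; two-sided 5% test.

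**The plan's own figure.** SE = 3.3 × √(2/36) = 0.778. Noncentrality = 2.5/0.778 = 3.21 on 70 df, giving 88.7% power by the noncentral t (89.5% by the normal approximation). The plan states at least 90%. The figure is reproduced to within rounding and is not the issue here.

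**Effect of an unadjusted imbalance.** The documents give no covariate effects, so two quantities are assumed: a covariate explaining 10% of the within-cohort variance in change (correlation √0.10 = 0.316), and a difference of d SD in its mean between cohorts.

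Shift in the estimate = 0.316 × d × 3.3. Type I error is the two-sided rejection rate when the true effect is zero. Adverse power is the rejection rate when the true 2.5 points is reduced by the shift.

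| d | Shift (points) | Shift/SE | Type I error | Adverse power |
|---|---|---|---|---|
| 0.25 | 0.26 | 0.34 | 6.3% | 81.0% |
| 0.5 | 0.52 | 0.67 | 10.1% | 70.8% |

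A simulation of 10,000 trials per setting agrees for the t-test (6.2% and 10.3%; 81.1% and 70.5%). With the covariate in a linear model, type I error was 4.8% and 5.1%, and adverse-direction power 90.1% and 88.7%. That recovery occurs because the simulated confounder is in the model. It says nothing about confounders left out.

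**Cost of adjusting.** With three covariates the residual df are 72 − 5 = 67, and SE = 0.778 × √((1 − R²y)/(1 − R²c)). R²y is the outcome variance the covariates explain. R²c is how far they predict cohort membership. Both are assumed.

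| R²y | R²c | SE | Power at 2.5 points |
|---|---|---|---|
| 0 | 0 | 0.778 | 88.6% |
| 0 | 0.1 | 0.820 | 85.2% |
| 0 | 0.2 | 0.870 | 80.9% |
| 0.1 | 0 | 0.738 | 91.6% |
| 0.2 | 0 | 0.696 | 94.3% |

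**The case against.** The strongest reply is that the harm is hypothetical. No imbalance is documented, and neither is any prognostic effect of age, sex or baseline fat on fat gain. That stands, and it is why the figures above are illustrations.

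The one imbalance that can be partly gauged is small. Suppose the 48% overweight or obese in section 3.0 also described the 36 controls, which is not stated. The lowest permitted study mix (39%) would then differ by about 0.18 SD. With the same 10% assumption the shift is 0.316 × 0.18 × 3.3 = 0.19 points, type I error 5.7% and adverse power 83%. At 18/18 the difference is about 0.04 SD. Section 13.1 also argues that fat gain occurs whatever the starting composition, and plans to look at lean subjects separately. So weight was considered, although gain in every group is not equal gain, and no method is given.

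The missing control details may be held in the earlier CHLA study mentioned in 9.3. The study is also small and foresees a randomised Phase III trial, which limits the consequences. Both points are fair, but neither supplies a primary analysis.

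A reader might try to infer from the SDs in 3.0 and 13.2 how strongly baseline fat predicts gain. Those sections have not been reconciled, so the calculation supports neither side. A reader might also project a large scan-timing bias from the 10.4-point rise in 3.0 (23.3% to 33.7%). That figure conflicts with the relative increase of about 25% given in the same section, with the range in 2.2, and with the 5.5 points in 13.2. It is no basis for a magnitude; the discrepancy is a separate matter to reconcile.

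**Conclusion.** The omission is clear from the text. The primary historical comparison has no stated covariate adjustment, although the authors planned adjustment for the secondary MRD comparison. It should be fixed, because the primary estimate is open to measurable cohort differences and the remedy is cheap.

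Confidence is high for the omission only. Under the assumed 10% of variance and a 0.25 to 0.5 SD imbalance, the distortion is 0.26 to 0.52 points against a target of 2.5. It could create an apparent benefit or hide a real one.

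Two stronger readings are tempting. One is that the cohorts do differ, or that the result will favour the intervention; the documents show neither. The other is that adjustment would make the 5% error rate secure. It would do so only for confounders in the model, and would leave calendar time, unmeasured factors and selection on ability to comply untouched.

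**What to change.** In 13.2, prespecify as the primary analysis a linear model of change in DXA body fat percentage on cohort, adjusted for baseline DXA body fat percentage and age, plus sex, once age and sex are confirmed for the 36 controls. Keep the unadjusted t-test as supportive.

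Add a CHLA-only sensitivity analysis. Where both datasets hold the data, add sensitivity analyses adjusting for days between scans and for steroid regimen. Section 9.1 says the baseline scan "must be done within 96 hours from the beginning of systemic chemotherapy" and that its timing is recorded, but control scan dates are not documented. Keep days between scans out of the primary model, because it is partly determined after the intervention starts.

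State whether the exclusions in 5.2 were applied to the controls. Describe the result as a historical comparison that adjustment cannot free of calendar-time effects or compliance selection.

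The cost is SAP wording plus a data check. Baseline DXA is held for both cohorts. The age range in 3.0 suggests that age was recorded for the earlier cohort, but age and sex must be verified for these 36. Steroid type and duration are not among the items listed in 9.1 and would have to come from charts. Power is 89% with balanced cohorts and 81% at a cohort R-squared of 0.2 if the covariates explain nothing. It rises to 92–94% if they explain 10–20% of the outcome variance and do not overlap with cohort.

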2.2 FAT MASS AND ALL

Obesity increases the incidence of many cancer types, and obese cancer patients have a higher risk of mortality from their disease (3). In 2007, a landmark study in the Children's Oncology Group (COG) led by [name] from the Children's Hospital Los Angeles (CHLA) demonstrated in two large cohorts (4,314 and 1,160 patients) that obesity at the time of diagnosis increases risk of relapse in children with National Cancer Institute/Rome High-Risk B-precursor ALL (HR-ALL) by 50% (1), a finding independently confirmed in a different population of children (7) in obese adults (8), and by meta-analysis (2). In a recent study, 36% of children with ALL were overweight or obese at diagnosis (9), while in another cohort 23% of children with HR-ALL continued to be obese throughout therapy (10). In our earlier cohort of adolescent and young adults with HR-ALL treated at CHLA, we found an even higher prevalence of high body fat whereas 48% were overweight or obese at diagnosis. Our data also showed that all individuals – both those lean and those obese- gain a significant amount of adipose tissue during the first month of treatment alone ("induction"). On average, patients gained ~20-30% of fat above their starting body fat percentage. The use of glucocorticoids such as dexamethasone and prednisone during induction therapy likely contribute to this fat gain, as they stimulate adipogenesis and appetite. Predisposition to inactivity due to intensive leukemia treatment combined with steroid-induced dietary derangements are therefore likely moderating factors of this marked gain in body fat. As response to leukemia treatment in the first month of therapy is a key determinant of overall prognosis and risk for relapse, and as obesity and body fat are risks factors for relapse, an intervention aimed at reducing the gain in body fat has potential to improve leukemia therapy efficacy starting from the initial time of diagnosis.

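### The primary-endpoint power in section 13.2 is slightly overstated: the named t-test gives 88.7%, not at least 90% (minor; wording only)

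*Combined protocol and SAP*

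**What the plan says.** Section 13.2 defines the primary endpoint as a smaller gain in DXA body fat percent from diagnosis to end of induction, compared with 36 historical patients at the coordinating centre. In those patients "there was a significant average fat gain during induction therapy of 5.5 ± 3.3 percent". The comparison is a two-sample, "two-sided t-test with 5% Type I error", with 36 subjects on each side, and the plan concludes that "there will be at least 90% power to detect a 2.5 percentage point reduction in change in body fat", for example a gain of 3.0 instead of 5.5. Section 13.1 supplies the study-side number, "for an effective sample size of at least 36 subjects", after allowing for subjects who are not enrolled or not evaluable.

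Section 3.0 describes adolescents treated at the same centre. It says that "subjects had an ~25% increase in body fat over these first 28 days of chemotherapy alone" and gives the means as "from $23.3 \pm 9.1\%$ at time of diagnosis to $33.7 \pm 9.8\%$ at end of induction".

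**The concern.** A power statement worded as a lower bound should be met by the test it names. Section 13.2 gives every input, so the claim can be checked directly, and it falls just short. At stake is the accuracy of the figure that justifies the primary comparison. The adequacy of the design is not in question.

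The secondary matter is consistency. The trial has no concurrent control, so readers look to the historical induction gain for context. The protocol prints two pairs of figures for that gain that do not agree, and the sentence in section 3.0 does not agree with itself.

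**Working it through.** **Inputs, all from section 13.2:** n = 36 per group; SD of change 3.3; difference 5.5 − 3.0 = 2.5 points; two-sided alpha 0.05; two-sample t-test. Section 13.1 confirms that 36 is already the evaluable number, so no further dropout deduction applies.

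**Power as stated**

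- Standard error of the difference: 3.3 × √(1/36 + 1/36) = 0.778.
- Noncentrality: 2.5 / 0.778 = 3.214, with 36 + 36 − 2 = 70 degrees of freedom.
- Normal approximation: Φ(3.214 − 1.960) = Φ(1.254) = 89.5%.
- Exact t (noncentral t, 70 df): **88.7%**.
- A one-sided 5% t-test would give 93.8%, but the plan specifies two-sided.

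**Could rounding of the SD rescue the claim?** An SD printed as 3.3 lies between 3.25 and 3.35.

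| SD | Exact t | Normal approximation |
|---|---|---|
| 3.25 | 89.6% | 90.4% |
| 3.27 | 89.2% | 90.0% |
| 3.30 | 88.7% | 89.5% |
| 3.35 | 87.7% | 88.6% |

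Exact t needs an SD of 3.227 or less, which would print as 3.2. The normal approximation reaches 90% only if the unrounded SD is about 3.27 or less.

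**What would give 90% by exact t, for scale only:** a difference of 2.557 points at 36 per group; or 38 per group (90.3%; 37 gives 89.5%); or 40 study subjects against the 36 historical (90.2%; 38 gives 89.5%).

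**Section 3.0 figures**

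- Absolute rise: 33.7 − 23.3 = 10.4 points (10.3 to 10.5 allowing for rounding).
- Relative rise: 10.4 / 23.3 = 44.6%, against about 25% in the same sentence.
- A 25% rise from 23.3 would end at 23.3 × 1.25 = 29.1. A 25% rise ending at 33.7 would start from 33.7 / 1.25 = 27.0. Neither matches the printed pair.
- Gap to section 13.2: 10.4 − 5.5 = 4.9 points.

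The power formula uses only the SD of change, the 2.5-point difference and the two sample sizes. Neither section 3.0 mean enters it.

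**The case against.** On power, the normal approximation gives 89.5%, which rounds to 90%, and a shortfall of 1.3 points is within what many statisticians would accept as reproducing the figure. Section 13.1 also states its accrual figures as minimums. Forty evaluable subjects out of 45 would be 89%, consistent with more than 85% evaluable, and would give 90.2%. These points show that the issue is small and changes no decision. They do not rescue the wording: section 13.1 sets the goal at 36, section 13.2 computes with 36 against 36 and names a t-test, and at those values the stated floor is not met.

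On section 3.0, a digit may have been misread from the PDF, and Fig. 1, which plots these data, is not visible in the available text. The text does not say that the two means come from the same patients at both times, nor that they are the 36 patients of section 13.2. Either could explain the disagreement, so it is a query and not an established sponsor error.

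A reader might go further in three ways, none of which the documents support:

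- **That a particular mean is wrong.** Section 2.2 says "On average, patients gained ~20-30% of fat above their starting body fat percentage", and it is tempting to use this with the 5.5-point gain to pick the faulty figure. But any such match takes one of the doubtful section 3.0 means as its base, so the reasoning is circular.
- **That the kilogram figure settles it.** Section 3.0 adds that "this increase in body fat represents a gain of 5.2 ± 4.9 kg of adipose tissue over the entire study period". Turning percentages into kilograms needs body weights at each time, which the documents do not give.
- **That the 5.5-point reference or the SD of 3.3 is unsound, so the trial is underpowered.** Section 13.2 reports both directly, from patients with scans before and after induction. The SDs of 9.1 and 9.8 in section 3.0 would imply a pre/post correlation of (9.1² + 9.8² − 3.3²) / (2 × 9.1 × 9.8) = 0.94 if they came from the same patients. The documents give no correlation that contradicts this.

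**Conclusion.** The power statement is wrong as written, but only slightly: 88.7% by the named test against a claim of at least 90%. This rests solely on the inputs in section 13.2 and holds across the rounding range of the SD at a 2.5-point difference. It has no sample-size or design consequence. Confidence in the arithmetic is high.

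The section 3.0 mismatch is a secondary consistency note. As printed, 10.4 points or 45% does not fit about 25%, and the text does not relate it to 5.5 points. Whether this is a misread digit, a reporting error or a different patient set cannot be decided from the documents. Section 13.2 names its own comparator, so the mismatch leaves the planned test, its power and the effect estimate as they are.

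**What to change.** In section 13.2, replace the lower bound with either about 89% power for a 2.5-point reduction or 90% power for a reduction of about 2.56 points. Keep the target of 36 evaluable subjects. The cost is one sentence and a stated power about one point less favourable.

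For section 3.0, check the digits of the two means in the original PDF and Fig. 1, then against the historical DXA data. Correct whichever figure is wrong, or state that the patient set differs from the 36 in section 13.2. The cost is a look-up in data already held and a correction or short note.
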